### iFOUR

The Increase Individual Income and Independence program (iFOUR) is an employment program that was developed over ten years ago to target the employment needs of HIV- positive people. The program was based on the Supported Employment framework that was developed to help connect people with a range of disabilities (physical and cognitive) to employment because of the benefits of employment, both monetary and non-monetary. Thus, researchers at the University of Illinois-Chicago collaborated with Chicago House, a housing and support organization for HIV- positive individuals, to develop a Supported Employment program for HIV- positive individuals. Like Supported Employment, iFOUR provides a variety of supports to aid in participants' job success, such as job training referrals, client-tailored job placement, post-employment assistance, and benefits planning. The program includes regular interviews to evaluate program outcomes, such as medication adherence, use of drugs and alcohol, and assessments of physical and mental health. Since 2005, the iFOUR program has been refined to better tailor to the needs of HIV- positive individuals, including the addition of one-on-one work with a career specialist. These specialists assess job readiness and are trained in the impact of HIV/AIDS on employment, so as to best assist participants with their career aspirations. They also assist with linking participants to additional educational resources and provide support with interview preparation and development of resumes and cover letters. iFOUR also includes a four-week training workshop that is tailored to the needs of HIV- positive participants, dealing with questions such as workplace discrimination, benefits maintenance, and the relationship of health beliefs and work. The workshop also covers confidence and communication skills, while highlighting the non-monetary benefits of employment. The iFOUR program has had positive outcomes for participants, documented in several studies (Appendix IV). The goal of the current study is to tailor then pilot test the iFOUR program for individuals who are HIV-negative but at high-risk for acquiring HIV.

### 5.2.3 Research Staff Training

Prior to engaging in any study specific activities, staff must complete study trainings as outlined below:

- GCP training
- Human Subjects Protection training
- W2P Workshop Facilitator Training: Members of the research team who facilitate workshop sessions will be trained by staff who have run the iFOUR program. This training includes an overview of how iFOUR was implemented, challenges in implementation, and best practices for ensuring the utility of career readiness training.
- Title IX Training: All staff will complete annual Title IX training in the prevention of sexual assault and sexual misconduct via "Intersections: Preventing Harassment and Sexual Violence"
- Suspected Child Abuse Reporting Training: All staff will review guidelines related to their status as mandated reporters of suspected child abuse and neglect if applicable by state law.

Additionally, staff may opt to complete the web-based training "Recognizing and Reporting

Child Abuse: Training for Mandated Reporters,” which defines when mandated reporters must contact Child Support Services if abuse or neglect is suspected.

- HIV Testing Training: Staff engaged in the collection of biological samples will complete a 4 hour specialized training on HIV client-centered counseling techniques, HIV prevention strategies, and other sensitive issues through the Midwest AIDS Training and Education Center.
- Ready Set PrEP! Training: All staff will complete training regarding HIV prevention and PrEP access through the AIDS Foundation of Chicago’s (AFC) “Ready Set PrEP!” This training focuses on how antiretroviral medication can be used for prevention of HIV transmission and how social determinants of health impact PrEP access.

#### 5.2.4 Intervention Monitoring/Quality Control

Research staff running the workshops will complete fidelity assessments during administration of each workshop class to help ensure and evaluate homogeneity across workshop groups. In addition, workshop staff will conduct a debriefing session after the administration of each workshop class in order to note any issues or observations.

### 6.0 EVALUATIONS AND MEASURES

The study procedures will unfold in three phases, outlined below.

#### Phase 1

Focus groups and key informant interviews will be conducted. Focus group participants will be asked to discuss perceived barriers to employment, beliefs in the benefits of employment, and career counseling needs of YMSM and YTW of color. Participants will also be asked to review key components of models of the adapted iFOUR employment curriculum to gauge relevance and potential modifications. Key informant interviews will be conducted and the topics covered in will be similar to the focus groups, while allowing for more in-depth investigation of individual experiences.

#### Phase 2

Based on the data collected during phase 1, we will develop the adapted employment intervention and complete an initial pre-test consisting of the Baseline visit, workshops, and Post-Intervention visits. We will then pilot the intervention with participants in a single-arm longitudinal pre-/post-study. At Baseline, participants will complete a 30-60 minute audio-computer assisted self-interview (ACASI) survey covering sociodemographics, employment variables, HIV risk behavior variables, and potential modifying variables. Participants will also be asked for biological specimen collection for HIV/STIs screening and drug testing (such as urine, oral/laryngeal swab, finger stick, and anal swab). Upon completion of the employment intervention at Post-Intervention, participants will be asked to complete a second 30-45 minute ACASI survey regarding employment variables, HIV risk behavior variables, as well as the feasibility, acceptability and satisfaction of the program. After 8 months post-intervention, participants will be asked to return to the study site to complete the Follow-Up visit and repeat ACASI survey assessing sociodemographics, employment variables, HIV risk behavior variables, and potential modifying variables, as well as to provide repeat biological specimens for HIV/STIs screening and drug testing.

#### Phase 3

We will further adapt study procedures and the employment intervention so that it may be administered in community-based settings. All study procedures for Phase 3 are same as Phase 2 except that the Follow-Up visit is at 3 months follow-up, and the ACASI surveys are shorter in length at 20-45 minutes each visit.

## 6.1 Pilot-Test Screening

Interested participants will be pre-screened for eligibility by the ATN 151 Screening Form, either via phone with study staff or online via a Qualtrics survey. Participants who are eligible at pre-screen will then be scheduled for their Baseline study visit.

After informed consent, participants will be assigned a SID and then asked items from the ATN 151 Eligibility Form to confirm that the participant meets study criteria.

Table 1: Description of variables to be collected at each of the three study time points.

Study visits	Variables collected
Baseline Visit (T1)	Sociodemographics, employment variables, HIV risk behavior variables, and potential modifying variables HIV/STI screening and drug testing
Workshop Intervention	Workshop fidelity and debriefing
Post-Intervention Visit (T2)	Employment variables, variables assessing feasibility, acceptability, and satisfaction of intervention, and HIV risk behavior variables
Follow-up Visit (T3) Phase 2: 8 Months Phase 3: 3 Months	Sociodemographics, employment variables, HIV risk behavior variables, and potential modifying variables HIV/STI screening and drug testing

## 6.2 Baseline/Enrollment

After informed consent and eligibility has been confirmed, participants will undergo biological specimen collection for HIV/STIs screening and drug testing. Please note that for Phase 3, if a participant has a known positive HIV status they will not undergo HIV testing. Participants will be given an iPad tablet and headphones and asked to complete an ACASI survey. The survey includes items on: sociodemographics, employment variables, HIV risk behavior variables, and potential modifying variables including perceived transgender discrimination scale, job seeking self-efficacy, managing interview, resilience, employment and job search, integrated motivations, internal self-concept, goal internalization, perceived social support, drug use, alcohol use, sexual history, commercial sex work, homelessness, condom intentions, money inventory, and PrEP awareness.

## 6.3 Workshop Intervention

After the Baseline visit (T1), participants have up to 12 weeks to complete workshop classes for Phase 2 and up to 4 weeks for Phase 3, otherwise they will go on to complete the T2 and T3 visits. Participants who do not complete any workshop classes may still complete the T3 visit.

## **6.4 Post-Intervention**

At the completion of the workshop intervention, participants have 0-2 weeks to complete the post-intervention visit (T2). Participants will complete an ACASI survey assessing the feasibility, acceptability, and satisfaction of the program, as well as employment variables such as perceived discrimination, job self-efficacy, managing interviews, resilience, employment and job searching, motivations, goal setting, financial planning, and variables such as perceived social support, drug and alcohol use, sexual history, sex work, housing situation, condom use, and HIV risk behaviors.

## **6.5 Intervention Follow-Up**

For Phase 2 the follow-up visit (T3) is scheduled for 8 months post-intervention ( $\pm 4$  weeks), and for Phase 3 the follow-up visit is scheduled for 3 months post-intervention ( $\pm 2$  weeks). At this visit, participants will repeat biological specimen collection for HIV/STIs screening and drug use. If a participant already has a known positive HIV status they will not undergo HIV testing. Participants will repeat the ACASI survey with items on sociodemographics, employment variables, HIV risk behavior variables, and potential modifying variables such as perceived transgender discrimination scale, job seeking self-efficacy, managing interview, resilience, employment and job search, integrated motivations, internal self-concept, goal internalization, perceived social support, drug use, alcohol use, sexual history, commercial sex work, homelessness, condom intentions, money inventory, and PrEP awareness.

# **7.0 DATA COLLECTION AND SITE MONITORING**

## **7.1 Development of Protocol and Case Report Forms**

The ATN CC, in collaboration with the Protocol Team, is responsible for the development of this protocol as well as the Case Report Forms (CRFs) and Audio Computer-Assisted Self Interview (ACASI). All CRFs for this study will be available for download from the ATN study website.

## **7.2 Data Records**

Participant-related study information will only be identified through a SID which will be on all participant CRFs and ACASI response files. Participant names or other personally-identifying information will not be used on any study documents except that contact information approved by the study participant will appear on study contact forms and reports, which will be securely maintained by both the site and the CC. All study-related information will be kept in double-locked, limited access areas at the study site. A log that links the names of participants to their SID number will also be kept under double locks and separate from all other research records, accessible only to the study staff, ATN site monitors, and representatives from the NICHD. Original source documents for individual participants will be maintained at the study site and will be accessible only to the study staff. Data from original source documents will be transcribed on CRFs as applicable.

Individuals who complete the pre-screening process but who do not consent to participate will only have information collected on the ATN 151 Screening Form, which will be entered into the study database using a method to maintain anonymity.

## **7.3 Data Collection and Submission**

Research staff will be responsible for ensuring that CRF data is entered into CDART within one calendar week of data collection in a timely manner. Data edits through range checks and field inconsistencies will

be built into the CDART database to enable real time correction of key entries and CRF completion errors.

All data collected using ACASI will be developed within the CDART web-based system. The participant's SID will be used in order to link the interview responses to the participant's CRF data. The ACASI data will be collected on Apple iPad devices using Qualtrics and the CDART data management tool. Data are stored on secure servers maintained by the ATN CC. No data is written to the iPad hard drive. Since data are persisted to the secure servers during data collection, if a network failure occurs during an interview little to no data will be lost. The secured servers comply with FIMSA regulations and are tightly controlled, and inaccessible to any person or application without appropriate credentials.

Focus group and key informant interviews will be digitally audio-recorded with participant consent. Immediately upon completion, the digital audio files will be uploaded to a secure server. The audio recordings will be uploaded to a secure website belonging to a transcription company (CastingWords), who will listen to the recordings, transcribe them into a Microsoft Word file, and upload the transcript files to their secure website for download by study staff. Transcripts will be checked against audio recordings for accuracy. Once that process is complete, the audio files will be destroyed. [name] will ensure that the audio files are destroyed by the transcription company, and permanently deleted from the University of Chicago OBGYN server.

Data from focus groups and key informant interviews will be transferred to the ATN CC. This data and all data collected using CDART will be submitted to the NICHD's Data and Specimen Hub (DASH) after completion of the study in accordance with the NICHD DASH Data Archive Policy (<https://dash.nichd.nih.gov/Resource/Policies>) and the NIH Grants Policy Statement (<https://grants.nih.gov/grants/policy/nihgps/HTML5/introduction.htm>).

## **7.4 Data Quality Assurance**

Investigators receiving federal funding must adhere to the Code of Federal Regulations (CFR) to protect research participants and produce reliable study information. Sites participating in research sponsored by the NICHD need to have an internal Quality Assurance (QA) plan that will identify problems and correct errors in research study records. ATN sites will specify their QA plan at protocol registration in the Protocol Implementation Plan.

## **7.5 Role of Data Management**

The CC will provide instructions concerning ACASI administration, the recording of study data on CRFs, data entry, and data transmission to the CC via CDART at the completion of the study. It is the responsibility of the CC to assure the quality of computerized data. This role extends from protocol development to generation of the final study databases.

## **7.6 Study Site Monitoring and Record Availability**

Site monitors from the CC will visit participating study sites to review participant records, ICFs, CRFs and supporting source documentation, compliance with the protocol, and the accuracy and completeness of records. Regulatory files, as required, will also be inspected to ensure that regulatory requirements are being followed.

The site investigator will make study documents (e.g., CRFs, ICFs) and *pertinent source records* readily available for inspection by the local IRB, the site monitors, the NICHD, the Office of Human Research Protection (OHRP), or the sponsor's designee for confirmation of the study data.

## **8.0 PARTICIPANT MANAGEMENT**

### **8.1 Tracking Participants / Follow-up**

Site study staff will track participant study recruitment and retention for all study visits, as well as intervention sessions completed by participants.

### **8.2 Study Visit Management**

After the Baseline visit, participants have up to 12 weeks to complete workshop classes for Phase 2 and up to 4 weeks for Phase 3, otherwise they may go on to complete the post-intervention and follow-up visits as outlined below. Participants who do not complete any workshop classes may still complete the follow-up visit. Participants may withdraw from the study at any time, and may be considered lost to follow up if they are unable to be reached after a minimum of three documented contact attempts.

- For participants that complete all 4 workshop sessions, the post-intervention visit will need to be completed w/in 2 weeks of the last workshop session, otherwise they may go on to complete the follow-up visit at 8 months ( $\pm 4$  weeks) after the last workshop session for Phase 2 and at 3 months ( $\pm 2$  weeks) for Phase 3.
- For participants that complete at least one but less than all four of the workshop sessions in the time allowed (within 12 weeks of baseline for Phase 2, and 4 weeks for Phase 3), the post-intervention visit will need to be completed within 14 weeks of Baseline for Phase 2 and within 6 weeks for Phase 3. Otherwise, participants may go on to complete the follow-up visit at 8 months of the last class completed ( $\pm 4$  weeks) for Phase 2, and 3 months of the last class completed ( $\pm 2$  weeks) for phase 3.
- For participants that do not complete any workshop sessions, the follow-up visit will need to be completed at 8 months ( $\pm 4$  weeks) after Baseline for Phase 2, and 3 months ( $\pm 2$  weeks) for Phase 3.

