5.4. Analysis of Primary Outcomes

Primary outcomes for analyses include Information Systems Success Model score, workshop completion, change in Job-Seeking Self Efficacy Scale score, Protean Career Attitudes Scale score, change in Self-Directed Attitudes Scale score, and change in Values-Driven Attitudes Scale score. Details about these outcomes are described in Section 4.1.

Univariate analyses will be performed as described in Section 5.1. To the extent that data allows, multivariable analyses will adjust for sociodemographic characteristics, workshop attendance, baseline employment status, and study completeness. Analytical models will include linear regression or generalized linear models for continuous outcomes and logistic regression for binary and categorical outcomes.

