1.2. WORKSHOP COMPLETION

Workshop completion will be used in the assessment of intervention feasibility. The primary outcome for workshop completion will be measured using a binary outcome of Complete vs. Not Complete (1.2.2), but the number of completed workshops (1.2.1) is also defined to assess potential dose response of the workshop intervention on other outcomes.

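### T3 is timed from the last class for attenders but from Baseline for non-attenders, so any contrast of none versus at least one workshop in T1–T3 change is partly confounded with elapsed time

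*Protocol*

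**What the plan says.** Protocol 8.2 (Study Visit Management) gives three rules for T3.

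- All four sessions attended: 8 months "after the last workshop session for Phase 2 and at 3 months" in Phase 3, counted the same way.
- One to three sessions attended: "participants may go on to complete the follow-up visit at 8 months of the last class completed", and 3 months from that class in Phase 3.
- No session attended: "the follow-up visit will need to be completed at 8 months", counted "after Baseline for Phase 2, and 3 months" in Phase 3.

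The windows are ±4 weeks in Phase 2 and ±2 weeks in Phase 3. Protocol 6.3 sets how late the last class can be: "participants have up to 12 weeks to complete workshop classes for Phase 2 and up to 4 weeks for Phase 3".

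Both SAPs (3.1) include everyone who completes T3 in the T1–T3 change analyses, so non-attenders are in. Section 5.4 states that "multivariable analyses will adjust for sociodemographic characteristics, workshop attendance, baseline employment status, and study completeness"; section 5.5 does the same for the secondary outcomes. Appendix 1.2 adds that the number of workshops attended "is also defined to assess potential dose response of the workshop intervention on other outcomes". Neither SAP nor Protocol 10.3 has a term for time since Baseline. Both SAPs (2.1) describe T3 only as a post-intervention visit and do not mention the Baseline origin for non-attenders.

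**The concern.** The two origins give attenders and non-attenders different target intervals between T1 and T3. Participants enter either unemployed and seeking work or working part-time (Protocol 4.1.4 and 4.1.5), so weekly hours could plausibly rise with time whatever the workshops do. A model that contrasts attenders with non-attenders and omits the interval would credit that rise to attendance. With no comparison group, a relation between attendance and outcome is one of the few internal signals of efficacy the pilot can offer. An analyst working only from the SAPs would not know that the origins differ.

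**Working it through.** **1. Check of the maximum delay.** Protocol 8.2 gives partial attenders a T2 deadline counted from Baseline. Class window plus the 2-week T2 window: 12 + 2 = 14 weeks (Phase 2) and 4 + 2 = 6 weeks (Phase 3). Both match the stated deadlines, so 12 and 4 weeks are the right maxima.

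**2. Target T1–T3 interval.** Let M be the follow-up period and L the time from Baseline to the last class. One month is 365.25/7/12 = 4.35 weeks, so M = 34.8 weeks (8 months) or 13.0 weeks (3 months). A non-attender's target is M; an attender's is M + L.

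| | Non-attender target (with window) | Attender target (with window) | Target gap |
|---|---|---|---|
| Phase 2 | 34.8 (30.8–38.8) wk | 34.8–46.8 (30.8–50.8) wk | 0–12 wk |
| Phase 3 | 13.0 (11.0–15.0) wk | 13.0–17.0 (11.0–19.0) wk | 0–4 wk |

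The gap is at most 12/34.8 = 34% of the Phase 2 interval and 4/13.0 = 31% of the Phase 3 interval. The documents do not say how long after Baseline the classes start, so the typical gap is unknown.

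**3. Size on a job-finding scale.** The documents give no job-finding rate. Assume h = 3% to 8% per month regardless of attendance, with no job loss. The proportion who have found work by t months is 1 − (1 − h)^t. Differences are taken before rounding.

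| Phase 2 gap | h = 3% | h = 8% |
|---|---|---|
| 0 (8 months) | 21.6% | 48.7% |
| 2 weeks | 22.7% (+1.1) | 50.6% (+1.9) |
| 7 weeks | 25.4% (+3.8) | 55.1% (+6.4) |
| 12 weeks | 27.9% (+6.3) | 59.2% (+10.5) |

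Phase 3 at the 4-week maximum: 8.7% to 11.3% (+2.5) and 22.1% to 27.9% (+5.8). A 1-week gap gives +0.6 and +1.5.

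**4. Size on the SAP's scale, weekly hours.** The bias in an attender versus non-attender contrast is roughly drift × gap. For an assumed drift of 0.05 to 0.5 hours per calendar week, the bias is 0.1–1.0 h at 2 weeks, 0.35–3.5 h at 7 weeks and 0.6–6 h at 12 weeks. In Phase 3 at 4 weeks it is 0.2–2.0 h.

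**5. Can the two be separated?** Let p be the share attending, g the mean gap and w the window half-width, with T3 uniform in its window. The correlation of attendance with elapsed time is

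r = g√(p(1−p)) / √(w²/3 + p·Var(L) + g²p(1−p)).

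For Phase 2, with w = 4 and p assumed to be 50–90%:

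- last class at week 2 for all (g = 2): r = 0.25–0.40
- last class uniform over weeks 2–12 (g = 7): r = 0.51–0.75
- last class at week 12 for all (g = 12): r = 0.84–0.93

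Variance inflation is 1/(1 − r²): 1.07 at r = 0.25 and 7.4 at r = 0.93. Within the windows, an attender and a non-attender can share an interval only if L − 4 ≤ 4, that is, if the last class falls by week 8 in Phase 2. In Phase 3 the condition is L ≤ 4, which always holds.

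**The case against.** Much of the case on the other side stands.

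- **The main tests do not make this contrast.** SAP 5.1 plans paired T1–T3 tests in a single arm. A reader might infer that the two origins bias the main efficacy results. They do not; the pooled change only mixes interval lengths. The per-protocol population (SAP 3.2) and the Protocol 10.4 sensitivity analysis that excludes incomplete attenders contain only participants timed from their last class.
- **A gradient over one to four workshops does not follow.** A reader might infer that the interval lengthens with each workshop. Full and partial attenders share the same origin, so one late class can give a longer interval than four early ones. Only none versus at least one follows from the text.
- **The dose response is only a possibility.** No such model is specified, and SAP 4.1.2 assigns the session count to exploratory use.
- **Not every outcome is exposed.** The sexual-risk items use fixed recall (6 months in Phase 2, 3 in Phase 3), and the chlamydia and gonorrhoea tests show status at the visit. A longer interval moves the date of measurement without lengthening the recall period.
- **The larger figures are ceilings.** The planned delivery is over 2 weeks in Phase 2 and 2 days in Phase 3 (SAP 2.1), although the start may lag Baseline. Having found work is also not the SAP outcome. Allowing an assumed 5–10% monthly job loss among participants who start unemployed lowers the 12-week figure to about 2.4–6.4 points.
- **Timing from the last class is defensible.** It holds time since the intervention constant among attenders.

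None of this removes the remaining gap: the attendance models in SAP 5.4 and 5.5 include non-attenders and omit elapsed time.

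**Conclusion.** The concern holds for one kind of result: contrasts of none versus at least one workshop in T1–T3 change, whether through the attendance covariate or an exploratory dose response. The difference in target intervals, 0–12 weeks in Phase 2 and 0–4 in Phase 3, follows directly from the protocol. The resulting bias is unknown, because it depends on when classes finish and on whether the outcome drifts; the documents give neither. Hours worked is the most plausible case, with the attitude scales possible.

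Under the job-finding assumption, the spurious Phase 2 difference is about 1–2 points at 2 weeks, 4–6 at 7 weeks and 6–11 at the maximum; in Phase 3 it is at most about 3–6. A reader might take 6–11 points as the expected bias, but that needs every attender to finish in week 12 and nobody to lose a job. This is a low-cost improvement to the secondary modelling and reporting. It is not a fault in the visit schedule.

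**What to change.** In both SAPs:

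1. Tabulate the actual T1–T3 interval in days by number of workshops attended (0 to 4).
2. For T1–T3 change outcomes only, report each model containing attendance (5.4, 5.5 and any dose-response analysis) with and without the actual days from T1 to the outcome assessment. Leave out the ISSM score and workshop completion: these are T2 outcomes, and days to a later visit have no meaning for them.
3. For job-seeking self-efficacy, Appendix 1.3.4 uses the T2 score when T3 is missing. Use T1–T2 days for those participants.
4. State in SAP 2.1 that T3 is counted from Baseline for non-attenders.

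Visits and sessions are already tracked (Protocol 8.1), and applying the windows in 8.2 requires their dates, so the work is one table and one covariate. The real cost is precision: with at least 50 completers hoped for in Phase 2 and at most 40 enrolled in Phase 3, a variance inflation of about 1.1 to 7 widens the interval for the attendance coefficient, most where the gap is largest. For Phase 2 attenders whose last class is after week 8, the adjustment also extrapolates beyond any in-window non-attender. For both reasons the two versions should be shown side by side, with neither replacing the other.
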